## 4.2. Handling of missing data

As a single-centre study, this project has a low risk for missing data. All data will be recorded and safely stored on site. All efforts are being made with safety procedures in place not to lose any data during lab visits. In case of technical problems during data acquisition, the measurements will be repeated on the spot. In case of incomplete datasets due to withdrawal or drop-out, additional participants will be recruited until an adequate number of complete datasets (i.e.  $n=36$  for primary endpoint,  $n=12$  for secondary endpoint) are obtained.

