#### PHASE A: Screening, informed consent & baseline measurements.

- **1st Visit:** Screening, informed consent, health- and training-related questionnaire, allocation into three study groups (Group#1: no training, Group#2: 1 training per week, Group#3: 3 trainings per week). The approximate duration of the 1st Visit is **1h**.
- **2nd Visit:** Baseline measurements. 3D body surface scan, anthropometric measurements, ultrasound, isokinetic strength tests, iPhone/watchOS measurements and optical motion capture during exercise execution. The approximate duration of the 2nd Visit is **4h**. The time between the 1st and 2nd visit is defined within two weeks of the 1st visit to fit in with the participant's schedule.
- **MRI scan** (sub-group,  $n=12$ ): An additional visit is scheduled for the sub-group of  $n=12$  participants to obtain data from MRI of the lower limbs. The scan time is 10-15 minutes, with the total duration of the visit to the MRI facilities at the SCMI being approximately **30**

**minutes.** MRI data acquisition is individually defined within two weeks of the 1st visit to fit in with the participant's schedule.

PHASE B: 8-week strength training intervention. Conduct of an 8-week strength training intervention of key muscle-tendon groups associated with knee joint stability in the training-specific setting of each participant. Participants are randomly allocated into three study groups with increasing levels of loading (Group#1: no training, Group#2: 1 training per week, Group#3: 3 trainings per week) with the same number of subjects and gender distribution in each group ( $n=12$  per group, 6F and 6M). The same guidelines for the warm-up and the type of exercises will be given prior to the intervention study to each participant. Participants are asked to record exercise load and volume as well as monitor training-related variables and 1RM using the *iOS Strength Control app*. Participants perform the strength training self-directedly in their chosen fitness/training facilities as it fits into their weekly routine. Contact to the study investigator is ensured at all times in case of questions.

PHASE C: Post-intervention measurements.

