**Table 3.3.1.** Overall project plan, starting in first quarter of year 1 (May 2021)

	YEAR 1				YEAR 2				YEAR 3				YEAR 4			
Technology set-up and preparation																
Recruitment																
Data acquisition																
Data analysis																
Project management & reporting																

**Table 3.3.2.** Schedule of assessments

Time (weeks)	>-1 day	0	0-2	0-2	8-10
Goal	Info	Screening	Baseline	MRI	Post-intervention
Oral and written information	+				
Check inclusion-/exclusion criteria		+	+		+
Written consent		+			
Participant characteristics		+			
Health- & training-related questionnaire		+			
Anthropometric measurements ISAK			+		+
3D body surface scan			+		+
Ultrasound measurements			+		+
Isokinetic strength tests			+		+
iPhone/watchOS			+		+
Optical motion capture			+		+
MRI				+	(n=12)

**Table 3.3.3.** Summary table listing all project visits, duration, measurements, procedures and instructions to the participants.

TIME	MEASUREMENT	PROCEDURE/EXERCISE	INSTRUCTIONS
1 st Visit: Screening & informed consent (n=36)			

1 h	Informed consent Health- and training-related questionnaire	Inform about study protocol in detail, answer questions, check inclusion and exclusion criteria, assign participant ID, fill in health- and training-related questionnaire.	Participant to carefully read through informed consent and take time for questions and consideration to participate in this study. Participant to fill out consent form and questionnaire.
2nd Visit and 3rd Visit: Baseline measurements & post-intervention measurements (n=36)			
4h	Welcome	Outline procedure and double-check inclusion/exclusion criteria. Withdraw participant if health situation has changed.	Participant self-declares inclusion/exclusion criteria.
	Anthropometric data	Anthropometric measurements according to ISAK standards. 3D body surface scan in relaxed neutral position and image capture from frontal and lateral. Ultrasound of hamstrings and quadriceps according to established protocols at the Swiss Olympic Medical Centre	Participants to stand upright on marked location in relaxed neutral position. 3D body surface scan takes 5-10minutes. The participant is asked to stay as still as possible. Participants to sit upright with their lower limbs relaxed and supported in extended position.

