### 3.4 Withdrawal and discontinuation

Participants can withdraw from the study at any time without giving further reasons. A participant can also be withdrawn from the study if she or he does not comply to the instructions of the study personnel as outlined in Table 3.3.3 or the participant's health situation has changed between the initial screening and the training session due to unforeseen circumstances (i.e. exclusion criteria: acute musculoskeletal pain or injury).

If a participant is withdrawn from the study (or withdraws by herself/himself) during the schedule of assessments, only data gathered up to the point of withdrawal will be used for analysis.

All personal data is encrypted by assigning a unique participant ID to all experimental raw data and electronic data sheets, including analysis results. All data is stored on the secured server architecture at the SFSIM with restricted access to study staff only (see also Section 7).

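### Replacing post-randomisation losses until 36 complete datasets exist makes the between-group comparison a completer comparison, which can be biased in either direction

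*Combined protocol and SAP*

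**What the plan says.** - **Allocation and comparison.** Section 3.3, Phase B: "Participants are randomly allocated into three study groups with increasing levels of loading", with 12 per group (6 women, 6 men). Section 2.2 compares changes in 1RM, H:Q ratio, muscle volume and CSA between these groups.
- **Replacement.** Section 4.2: "In case of incomplete datasets due to withdrawal or drop-out", "additional participants will be recruited until an adequate number of complete datasets" are obtained, given as 36 for the primary endpoint and 12 for the secondary endpoint. It states no cap, no expected drop-out rate and no rule for allocating replacements.
- **Withdrawal for changed health.** Table 3.3.3 has one block for Visits 2 and 3. Its opening step, ahead of all measurements, includes "Withdraw participant if health situation has changed". Table 3.3.2 also marks an eligibility check post-intervention. Section 3.4 gives a different window: "health situation has changed between the initial screening and the training session due to unforeseen circumstances".
- **Withdrawal for non-compliance.** Section 3.4: "A participant can also be withdrawn from the study if she or he does not comply to the instructions of the study personnel", tied to the instructions in Table 3.3.3.
- **Data already collected.** Section 3.4: "only data gathered up to the point of withdrawal will be used for analysis". Section 7.3 says the same in substance.
- **Analysis.** Section 4.1 specifies a repeated measures ANOVA of predicted against measured values. It names no analysis population, no missing-data method and no model for the comparison between groups.

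**The concern.** Randomisation protects a comparison of everyone allocated. It does not protect a comparison of those who reach the end in good health, because both completion and health can be consequences of the assigned volume. New musculoskeletal pain during three sessions per week, or loss of interest among habitual trainees told not to train, are plausible examples. Pain is also an exclusion criterion, so the Visit 3 check can remove a participant just before the post-intervention outcome is taken. Recruiting until 12 complete datasets fill each group restores the numbers but not the comparability.

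Allocation takes place at Visit 1 and baseline measurement up to two weeks later, so even losses before baseline can depend on the group.

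At stake is the between-group comparison in a study that Section 2.3 calls confirmatory. Outcomes that are never collected after withdrawal cannot be recovered at the analysis stage.

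**Working it through.** **1. The plan's own figure.** Section 3.1 gives d = 1.5, alpha 0.025, power 0.9 and 11 per group, raised to 12. A two-sample t-test with noncentrality d·√(n/2) and one-sided alpha 0.025 needs n = 11 (power 91.7% at 11, 93.9% at 12), so 11 is reproduced. Read as two-sided 0.025, n = 13 is needed (85.3% at 11, 88.9% at 12). The plan does not state sidedness. The sample size arithmetic is not the problem here.

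**2. Reading the rules together.** Someone in Group#3 who develops knee pain in week 7 attends Visit 3, is found to have changed health and is withdrawn before measurement. The dataset is incomplete, so a further participant is recruited. The baseline record may be used under Section 3.4, but no method in Section 4.1 uses a baseline-only record in an analysis of change. In effect the change analysis contains only completers.

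**3. Size of the possible bias.** The documents give no loss rate, so every rate and correlation below is an assumption. Let a fraction q of an arm be lost, with staying correlated ρ with the outcome in SD units. The mean of those who stay then shifts by

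ρ × φ(z_q) / (1 − q).

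With ρ = 0.5 and loss of poorer responders in Group#3 only:

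- q = 10%: 0.5 × 0.1755 / 0.90 = 0.10
- q = 20%: 0.5 × 0.2800 / 0.80 = 0.175
- q = 30%: 0.5 × 0.3477 / 0.70 = 0.25

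A simulation that replaces until each arm has 12 completers (20,000 runs, true difference 1.5) agrees:

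| Assumed mechanism | Mean difference | Bias (SD) |
|---|---|---|
| Loss unrelated to response, 20% in both arms or in Group#3 only | 1.49–1.50 | 0 |
| Poorer responders leave Group#3; 10%, 20%, 30% | 1.60, 1.68, 1.74 | +0.10, +0.18, +0.24 |
| Group#3 loses exactly its lowest 20% | 1.85 | +0.35 |
| Same 20% loss and mechanism in both arms | 1.50 | 0 |
| Poorer performers leave Group#1 only, 20% | 1.33 | −0.17 |
| Better responders leave Group#3 only, 20% | 1.32 | −0.18 |

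With no true effect, a nominal two-sided 5% test rejects in 6.7% of runs when poorer responders leave Group#3 at 20%, in 9.4% at 30%, and in 14.5% when exactly the lowest 20% are lost.

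**4. The n = 12.** Section 2.2 compares changes in muscle volume and CSA across all three groups. Section 3.1 gives 36 complete datasets, with 12 participants having MRI at baseline. The 12 in Section 4.2 therefore fits only the MRI validation of muscle volume, not the whole secondary endpoint.

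**The case against.** The strongest defence is that the stated objective is prediction accuracy. The test written in Section 4.1 compares predicted with measured values within the same person. Replacement does not break randomisation for a paired test; it mainly narrows the sample to those who complete. That stands, and it limits the damage to the between-group comparison announced in Section 2.2.

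Several stronger readings are tempting, but the documents do not support them:

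- **That the rule inflates the training effect.** The table above shows zero and negative bias under mechanisms no less possible than the positive ones.
- **That participants who miss training are removed.** Withdrawal is discretionary and applies to someone who "does not comply to the instructions of the study personnel as outlined in Table 3.3.3". That table covers visit and measurement procedures; missed sessions are not a stated ground.
- **That withdrawn participants' data are discarded.** Sections 3.4 and 7.3 keep data up to withdrawal. The gap is the absence of a method that uses them.
- **That training-related complaints disappear.** Section 5.2 follows all adverse events. Complaints may leave the strength comparison, but not the safety record.
- **That replacements are placed predictably in the vacant group.** Fixed group sizes and gender mix make this a fair worry, but the rule is simply not stated.
- **That the effect would be overstated by 25%.** If 3 of 15 in Group#3 gained nothing and the 12 completers gained 30.2 kg (200.8 − 170.6, Section 3.1), the mean over all 15 would be 12 × 30.2 / 15 = 24.2 kg, a ratio of 1.25. But 30.2 kg is a single-arm pre-post change in rugby players, and the 3 of 15 is invented.

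**Conclusion.** The concern holds for the between-group comparison. Replacement after randomisation, together with a health-based withdrawal step placed before the Visit 3 measurements, gives a completer comparison selected on events that training volume can affect. Upward bias is plausible if overload complaints or poor response drive loss in Group#3, but neither direction nor size is established. Under the assumed mechanisms it runs from about −0.18 to +0.24 SD, reaching +0.35 SD in the extreme case, against a planning effect of 1.5 SD. These figures rest on assumed loss rates of 10–30% and, outside the extreme case, an assumed correlation of 0.5. With negligible loss, or loss unrelated to response, the bias vanishes. The predicted-versus-measured analysis is affected mainly through a selected sample.

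Two inconsistencies need correcting whatever the bias: the differing windows for health-change withdrawal in Section 3.4 and Tables 3.3.2 and 3.3.3, and the n = 12 for the secondary endpoint.

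**What to change.** In Section 4.2, with matching text in Section 4.1:

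- Define the primary between-group analysis set as all randomised participants in their allocated group.
- Fit a likelihood-based mixed model that keeps baseline-only records. Report the 36 completers as a sensitivity analysis.
- State that any later recruit is randomised by the same procedure, is not placed in the vacant group, and is analysed alongside the participant lost, not instead of them.
- Report losses and reasons by group, including losses between allocation and baseline.
- Seek Visit 3 data from every randomised participant who agrees, leaving participant safety decisions to the investigator. This matters most, because a mixed model relies on loss being explained by the observed data and cannot by itself correct loss driven by an unobserved response.
- Reconcile the health-change withdrawal window in Section 3.4 with the Visit 3 check in Tables 3.3.2 and 3.3.3.
- Apply n = 12 only to the baseline MRI validation of muscle volume, and n = 36 to the CSA and HMF volume changes compared across groups.

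**Cost.** Wording and a little more analysis. If recruitment stops at 36 randomised, completers and power fall: at d = 1.5 and two-sided alpha 0.025, from 88.9% at 12 per group to 80.9% at 10. This should be stated. To expect 36 completers, 36 / 0.90 = 40 would have to be randomised at an assumed 10% loss, and 36 / 0.80 = 45 at 20%.

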# 5 REGULATORY ASPECTS AND SAFETY

## 5.1 Local regulations / Declaration of Helsinki

This study is conducted in compliance with the protocol, the current version of the Declaration of Helsinki, Good Clinical Practice, the Clinical Trial Ordinance (ClinO) as well as other locally relevant legal and regulatory requirements. The study will be registered at the Swiss National Clinical Trials Portal (SNCTP).

## 5.2 (Serious) Adverse Events and notification of safety and protective measures

An Adverse Event (AE) is any untoward medical occurrence in a patient or a clinical investigation subject which does not necessarily have a causal relationship with the trial procedure. An AE can therefore be any unfavorable or unintended finding, symptom, or disease temporally associated with a trial procedure, whether or not related to it.

A Serious Adverse Event (SAE) (ClinO, Art. 63) is any untoward medical occurrence that

- Results in death or is life-threatening,
- Requires in-patient hospitalization or prolongation of existing hospitalization,
- Results in persistent or significant disability or incapacity, or
- Causes a congenital anomaly or birth defect

Both Investigator and Sponsor-Investigator make a causality assessment of the event to the trial intervention, (see table below based on the terms given in ICH E2A guidelines). Any event assessed as possibly, probably or definitely related is classified as related to the trial intervention.

Relationship	Description
--------------	-------------

Definitely	Temporal relationship Improvement after dechallenge* Recurrence after rechallenge (or other proof of drug cause)
Probably	Temporal relationship Improvement after dechallenge No other cause evident
Possibly	Temporal relationship Other cause possible
Unlikely	Any assessable reaction that does not fulfil the above conditions
Not related	Causal relationship can be ruled out
*Improvement after dechallenge only taken into consideration, if applicable to reaction	

Both Investigator and Sponsor-Investigator make a severity assessment of the event as mild, moderate or severe. Mild means the complication is tolerable, moderate means it interferes with daily activities and severe means it renders daily activities impossible.

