### **1.5. Risk category**

A (HRO art. 7). This project complies with the definition provided: „Ein Forschungsprojekt entspricht der Kategorie A, wenn die vorgesehenen Massnahmen zur Entnahme von biologischem Material oder zur Erhebung von Personendaten nur mit minimalen Risiken und Belastungen verbunden sind.“ The overall risk for participants is minimal, with the risk of harm due to the procedure itself being minimized by the design of the protocol.

All the methods and techniques that are used for data collection are non-invasive and hold minimal risks for participants. The strength exercises as part of the intervention study are identical with the exercises that are being performed in usual fitness and rehabilitation routines. Measurement methods include anthropometric measurements, 3D body surface scanning, ultrasound, isokinetic tests, optical motion capture, IMU measurements via the watchOS and a health- & training-related questionnaire; as well as MRI of the lower limbs in a sub-group of participants.

3D body surface data will be obtained using a structured light body surface scanner at the ZHAW, taking only a few seconds with extremely high accuracy between the scanned and the actual body volume without requiring any physical contact [37]. Anthropometric data will be acquired according to general athlete sports practice in line with recommended standards of the International Society for the Advancement of Kinanthropometry (ISAK). Ultrasound and isokinetic strength tests will be done according to established protocols at the Swiss Olympic Medical Centre but executed at the ZHAW. IMU measurements and optical motion capture require small reflective markers or sensors to be attached to the body surface. Possible skin irritations are very rare and can be locally treated (creams). MRI is the gold standard technique for musculoskeletal imaging without exposing the subject to harmful radiation [38]. In case a person feels uncomfortable inside the MRI tunnel due to claustrophobia or other reasons, the imaging can be discontinued anytime. The same holds for isokinetic tests, ultrasound, 3D body surface scanning and marker-based optical motion capture, should a participant feel uncomfortable or exhausted.

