#### **Reporting of SAEs (see ClinO, Art. 63)**

All SAEs are documented and reported immediately (within a maximum of 24 hours) to the Sponsor-Investigator of the study.

If it cannot be excluded that the SAE occurring in Switzerland is attributable to the intervention under investigation, the Investigator reports it to the Ethics Committee via BASEC within 15 days.

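### Section 5.2 ties causality and the 15-day Ethics Committee report to the intervention alone, so an SAE caused only by a study measurement can miss that report; its drug-based causality table also has a gap

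*Combined protocol and SAP*

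**What the plan says.** Section 5.2 uses two terms and defines neither.

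- **AE definition.** This is built on procedures. It covers findings "temporally associated with a trial procedure, whether or not related to it".
- **Causality.** This is built on the intervention: "Both Investigator and Sponsor-Investigator make a causality assessment of the event to the trial intervention". The rule that follows is "Any event assessed as possibly, probably or definitely related is classified as related to the trial intervention".
- **Causality table.** There are five categories. *Definitely* needs a temporal link, improvement on stopping, and "Recurrence after rechallenge (or other proof of drug cause". *Probably* reads "Temporal relationship Improvement after dechallenge No other cause evident". *Possibly* needs a temporal link and a possible alternative cause. *Unlikely* is the remainder: "Any assessable reaction that does not fulfil the above conditions". Only *Not related* means that causation is excluded. A footnote drops the dechallenge condition where it does not apply; its asterisk is printed only in the *Definitely* row.
- **SAE reporting.** Every SAE goes to the Sponsor-Investigator within 24 hours, whatever its cause. The 15-day report to the Ethics Committee has its own condition: "If it cannot be excluded that the SAE occurring in Switzerland is attributable to the intervention under investigation".

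Sections 1.4, 2.2 and 3.3 (Phase B) use the word intervention for the 8-week strength training.

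**The concern.** Every participant undergoes physically loading tests that are not part of the training. Table 3.3.3 lists isokinetic tests, drop jumps from a 30 cm box, counter-movement jumps and sprints with a cutting side step, and 12 participants also have an MRI. For Group#1, which has no training, these measurements are the only study activity.

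If causality is judged against the training alone, an SAE caused by one of them has no route to a related rating or to the 15-day report. What is at stake is whether the Ethics Committee hears promptly of harm from the tests.

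A second problem lies in the table. Its conditions were written for drugs, and this trial has none. Stopping and restarting a drug has no obvious counterpart for an acute injury, so the rating may turn on how a rater handles a condition that does not fit.

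**Working it through.** The plan gives no figure to reproduce. The check sets the rules side by side, counts the visits concerned and runs through the causality table.

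**1. Procedure versus intervention.** Take an SAE caused only by a measurement, at a visit where training cannot be the cause.

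- AE definition: met, because the event is associated with a procedure.
- Causality to the intervention: can be ruled out, so *Not related*.
- 24-hour report to the Sponsor-Investigator: required.
- 15-day report to the Ethics Committee: not triggered, because attribution to the intervention is excluded.

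The follow-up rule, the 7-day notice of immediate protective measures and the annual report (section 5.3) do not replace the 15-day report.

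**2. Visits concerned.** Inputs: 36 participants, 12 per group and 12 with MRI (sections 2.3 and 3.1); test visits 2 and 3 for everyone; visit 2 and the MRI in Phase A (section 3.3).

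- All procedure visits: 36 × 2 + 12 = 84.
- Training cannot be the cause: 36 (visit 2) + 12 (MRI) + 12 (Group#1, visit 3) = 60.
- Remainder: 84 − 60 = 24, the visit 3 tests of Groups #2 and #3. These fall within 7 days after the training period, so training may not be excludable and the trigger can still apply.

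**3. The causality table.** The event has a temporal link, and there is no rechallenge or other proof.

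| Improves on stopping | Other cause possible | Footnote covers both rows | Footnote covers *Definitely* only |
|---|---|---|---|
| Yes | No | Probably | Probably |
| Yes | Yes | Possibly | Possibly |
| No | No | **Unlikely** | **Unlikely** |
| No | Yes | Possibly | Possibly |
| Not applicable | No | Probably | **Unlikely** |
| Not applicable | Yes | Possibly | Possibly |

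In row three the event fails *Probably* for want of improvement and fails *Possibly* for want of another cause. Adding a competing cause (row four) raises it from unrelated to related. This holds under either reading of the footnote, and supplying proof of cause does not change row three. Row five depends on how far the footnote reaches.

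**4. Two thresholds.** The related label covers 3 of 5 categories (*Definitely*, *Probably*, *Possibly*). The Ethics Committee trigger, read literally, covers 4 of 5, because only *Not related* excludes causation. They differ on *Unlikely* alone.

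**The case against.** The other side has several good points.

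- **The two rules can both be followed.** The related rule sets a label and the trigger sets its own, wider test. A reader might infer that they contradict each other, or that a clear training injury could go unreported. The text does not support either: an *Unlikely* training SAE still meets the trigger. It would be missed only if staff used the label as the trigger.
- **The footnote is worded generally.** A reader might cite a tendon rupture during a study squat as an event forced into *Unlikely*. If dechallenge is regarded as not applicable and the footnote covers both rows, that event is *Probably*. Row three of the table remains.
- **Other safeguards exist.** All SAEs reach the Sponsor-Investigator within 24 hours, all are followed up, and procedure-related events are captured as AEs. What can be missed is the 15-day report.
- **Intervention is not defined in section 5.2.** A broad reading that includes the tests is possible. Usage elsewhere points to the training, and the AE definition's different term leaves the matter open. Section 5.2 cites the ordinance, but the documents do not reproduce its text, so it cannot settle the question here.
- **The named harms are mild.** Section 1.5 mentions skin irritation and claustrophobia, and says of the other measurements: "The same holds for isokinetic tests, ultrasound, 3D body surface scanning and marker-based optical motion capture, should a participant feel uncomfortable or exhausted". That concerns stopping a measurement and does not predict SAEs. Section 6.2 does, however, offer rest between measurements to limit fatigue or injury.

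**Conclusion.** The point stands in two parts.

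**Main part.** Causality and the 15-day trigger refer to the intervention only. Read literally, they leave measurement-caused SAEs at 60 planned visits outside prompt Ethics Committee reporting. This assumes that intervention means the 8-week training, that assignment to no training does not itself count as the intervention, that the MRI precedes training, and that all 36 participants complete. The 60 are visits, not expected events; the documents give no SAE rate. A reader might extend the gap to all 84 procedure visits, but at 24 of them training may not be excludable.

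**Second part.** The drug-worded table lets the absence of another cause lower a rating, and the scope of its footnote is unclear. The related label and the reporting trigger are misaligned on one category of five.

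A reader might also infer that a planned comparison of related events between groups would be wrong. Section 4 plans no such comparison. Endpoints, power and analysis are unaffected; this is a matter of safety reporting.

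**What to change.** Amend section 5.2 in three places.

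1. Assess causality against, and apply the existing 15-day trigger to, the training intervention or any study procedure. Record on the CRF which of the two is suspected.
2. State that the existing trigger, "If it cannot be excluded that the SAE occurring in Switzerland is attributable to the intervention under investigation", as widened in item 1 and so including events rated *Unlikely*, governs Ethics Committee reporting, and that the related label does not.
3. Reconcile the dechallenge and rechallenge conditions, the reference to a drug cause and the scope of the footnote with a trial that has no drug, so that the absence of another cause can never lower the rating. The exact criteria are for the sponsor to set; a fixed minimum rating for injuries is not needed to close the gap.

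The cost is a wording change, one extra CRF field and possibly a few more Ethics Committee reports.
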